### **10.3.2 Analysis of the primary pharmacokinetic variable(s)**

#### **10.3.2.1 Hypotheses and statistical model**

Not applicable.

#### **10.3.2.2 Handling of missing data**

Not applicable.

#### **10.3.2.3 Main analysis**

The observed PK data will be described by a population PK model using the same model structure as for the adult participants with PAH in the GRIPHON study [[Modeling and Simulation Report AC-065A302 \(GRIPHON\) 2014](#), [Modeling and Simulation Report, Pediatric dose selection 2016](#)]. This population PK model describes the PK of selexipag and ACT-333679 by 2-compartmental distribution models with linear elimination. Selexipag is absorbed by a first order process and part of the elimination from the central compartment is a metabolic transformation to form ACT-333679 [[Modeling and Simulation Report AC-065A302 \(GRIPHON\) 2014](#)].

The analyses will be performed to confirm or potentially revise the starting doses and up-titration increments for the next age cohort and the starting dose of the Phase 3 study.

#### 10.3.2.4 Supportive/sensitivity analyses

Not applicable.

#### 10.3.3 Analysis of secondary pharmacokinetic variable(s)

Plasma concentrations will be summarized per time point, by dose and body weight cohort using arithmetic mean, geometric mean, minimum, median, maximum, standard deviation (SD), standard error (SE), and two-sided 95% CI of the mean.

$AUC_{\tau,ss}$ ,  $C_{max,ss}$ ,  $C_{trough,ss}$ , and  $t_{max,ss}$  for selexipag and ACT-333679 based on NCA for selexipag and ACT-333679 will be listed and summarized by dose and body weight cohort, with arithmetic mean, geometric mean, minimum, median, maximum, SD, SE, coefficient of variation in %, and 95% CI of the arithmetic and geometric means.

Dose proportionality for  $AUC_{\tau,ss}$  and  $C_{max,ss}$  of selexipag and ACT-333679 will be explored by the power model as described by [Gough 1995].

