## 3 OVERALL STUDY DESIGN AND PLAN

### 3.1 Study design

This is a prospective, multi-center, open-label, single-arm Phase 2 study.

Approximately 60 participants will be enrolled in 3 different age cohorts (based on age at Baseline / Enrollment / Visit 2) to obtain at least 45 participants with evaluable PK profiles:

- Cohort 1:  $\geq 12$  to  $< 18$  years of age (approximately 20 enrolled participants to obtain at least 15 participants with evaluable PK profiles)
- Cohort 2:  $\geq 6$  to  $< 12$  years of age (approximately 20 enrolled participants to obtain at least 15 participants with evaluable PK profiles)
- Cohort 3:  $\geq 2$  to  $< 6$  years of age (approximately 20 enrolled participants to obtain at least 15 participants with evaluable PK profiles).

The starting dose is based on the body weight category of the participants, using the data from the population PK model in the GRIPHON/AC-065A302 study targeting the exposure observed in adult participants with PAH at a starting dose of 200 µg [[Modeling and Simulation Report AC-065A302 \(GRIPHON\) 2014](#)]. The continuous relationship between dose and body weight is used to define body weight categories and starting dose for each body weight category such that on average the exposure (combined exposure over one dosing interval at steady state [ $AUC_{\tau,ss,combined}$ ]) will be comparable to that in a 70 kg adult but not exceeding the exposure in a 50 kg adult [[Figure 1, Modeling and Simulation Report, Pediatric dose selection 2016](#)]:

[figure not shown]
- 100 µg for participants with a body weight from  $\geq 9$  to  $< 25$  kg.
- 150 µg for participants with a body weight from  $\geq 25$  to  $< 50$  kg.
- 200 µg for participants with a body weight  $\geq 50$  kg.

The body weight-exposure relationship is extrapolated from the body weight-exposure relationship determined by the population PK model in participants with PAH in the GRIPHON study with body weights ranging from 40–148 kg. In this model, body weight was a covariate on selexipag and ACT-333679 volume of distribution and elimination rate [[Modeling and Simulation Report AC-065A302 \(GRIPHON\) 2014](#)].

Confidential

**Figure 1** Estimated starting doses based on the GRIPHON PK model achieving the same exposure as in adult patients of 50 kg, 70 kg, and 96 kg treated with 200 µg b.i.d. selexipag

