### 3.2 Study design rationale

The objective of this pediatric study is to confirm the selexipag starting doses, selected by PK extrapolation from adults, that are expected to lead to similar exposure of selexipag and its active metabolite ACT-333679 in children as in adult PAH subjects (GRIPHON), following the same principle of up-titration to the iMTD. The primary PK endpoint is defined as exposure ( $AUC_{\tau,ss,combined}$ ) to selexipag and ACT-333679 corrected for potency, determined during the 12-week up-titration period. The PK parameters will be described with a population PK model and will be used to confirm/adjust the selected selexipag doses [Modeling and Simulation Report AC-065A302 (GRIPHON) 2014, Modeling and Simulation Report, Pediatric dose selection 2016]. The  $AUC_{\tau,ss,combined}$  in adult participants with PAH was also determined based on population PK modeling [Modeling and Simulation Report AC-065A302 (GRIPHON) 2014].

The following assumptions were used for the calculation of the starting dose in pediatric participants with PAH based on the GRIPHON model.

- In adults, the PK of selexipag and the active metabolite ACT-333679, after multiple-dose administration, are dose-proportional up to 1,800  $\mu\text{g}$ , given b.i.d. [Clinical Study Report AC-065A-101 2012, QGUY/2006/NS304/-01].
- It is assumed that the PK are also dose proportional in the pediatric population, and this will be further evaluated in the proposed study.
- The enzyme systems involved in selexipag metabolism (CES1, CES2, CYP2C8, UGT1A3, and UGT2B7), and CYP3A4, are essentially mature in children aged 2 years and older [Song 2017, Hines 2016, Smits 2012, McNamara 2002, Zhu 2009, Shi 2011, Yang 2009, Strassburg 2002, Oo 2003].
- No other major differences between the PK of selexipag in adults and children are expected.

The PK of selexipag and its active metabolite ACT-333679 in adult PAH subjects were characterized by a population PK model based on data from the GRIPHON study

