[[Modeling and Simulation Report AC-065A302 \(GRIPHON\) 2014](#)]. Body weight was identified as a statistically significant covariate for the volume of distribution of selexipag and ACT-333679, as well as for drug clearance. The model-predicted concentrations of selexipag and ACT-333679 for a reference subject of 70 kg were compared to model-predicted concentrations for subjects with body weights of 51 and 96 kg, corresponding to the 10th and 90th percentile of the body weight distribution of subjects included in the GRIPHON study, at steady-state doses of 1,600 µg b.i.d.

Compared to a 70 kg subject, a subject with a body weight of 51 kg is predicted to have 30% and 20% higher exposure to selexipag and to ACT-333679, respectively, whereas a subject with a body weight of 96 kg is predicted to have 20% and 10% lower exposure, respectively.

The selection of the starting dose for pediatric participants is based on body weight categories, using the data from the population PK model in the GRIPHON study, targeting the exposure observed in adult participants with PAH at a starting dose of 200 µg [[Modeling and Simulation Report AC-065A302 \(GRIPHON\) 2014](#)]. The exposure is defined as the combined exposure to selexipag and ACT-333679 corrected for potency ( $AUC_{\tau,ss,combined}$ ). The potency of ACT-333679 was estimated to be 37 times that of selexipag. ACT-333679 is, therefore, the major contributor to the efficacy of selexipag.

The continuous relationship between dose and body weight is used to define body weight categories and starting dose for each body weight category such that on average the exposure ( $AUC_{\tau,ss,combined}$ ) will be comparable to that in a 70 kg adult patient but not exceeding the exposure in a 50 kg adult patient [[Figure 1](#)].

The starting dose of selexipag expressed on a per kg basis increases in the lower body weight categories, as the relationship between body weight and dose is not linear. This is analogous with the pediatric experience with epoprostenol, where the doses in pediatric patients are generally higher than in adults on a per kg basis. However, assuming the body weight-to-exposure relationship observed in GRIPHON,  $AUC_{\tau,ss,combined}$  at the starting dose for pediatric patients in different body weight categories will not be higher than  $AUC_{\tau,ss,combined}$  at a starting dose of 200 µg b.i.d. in a 50 kg adult patient in the GRIPHON study.

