#### 5.1.4 Study drug starting dose and up-titration

At the Baseline/Enrollment visit, based on the participant's body weight, the body weight category, starting dose, and up-titration scheme will be determined.

Study medication administration will start in the evening of Day 1 and continue thereafter with b.i.d. dosing, i.e., in the morning and in the evening. During the up-titration period of 12 weeks, it is recommended that the doses are increased weekly in increments equal to the starting dose until the participants reach their iMTD or until a maximum dose corresponding to their baseline body weight category is achieved.

To improve tolerability, it is recommended that the study drug, selexipag, is taken with food and, at the beginning of each up-titration phase, that the first increased dose is taken in the evening. The maximum dose allowed to be administered will be 8-fold the corresponding starting dose:

- Body weight category  $\geq 50$  kg: starting dose of 200  $\mu\text{g}$  titrated up to the iMTD of 1,600  $\mu\text{g}$  b.i.d. Participants in this category will receive 200  $\mu\text{g}$  tablets only [Table 1].
- Body weight category  $\geq 25$  to  $< 50$  kg: starting dose of 150  $\mu\text{g}$  titrated up to the iMTD of 1,200  $\mu\text{g}$  b.i.d. Participants in this category will receive a combination of 50  $\mu\text{g}$  mini-tablets and 200  $\mu\text{g}$  tablets [Table 2].
- Body weight category  $\geq 9$  to  $< 25$  kg: starting dose of 100  $\mu\text{g}$  titrated up to the iMTD of 800  $\mu\text{g}$  b.i.d. Participants in this category will receive either a combination of 50  $\mu\text{g}$  mini-tablets and 200  $\mu\text{g}$  tablets, or 50  $\mu\text{g}$  mini-tablets only, if requested by the investigator [Table 3].

Two study-treatment supply options are available:

Option 1 will supply participants able to swallow tablets whole with water with a combination of 200  $\mu\text{g}$  tablets and 50  $\mu\text{g}$  mini-tablets to minimize the overall number of tablets per intake and will be provided via IRT by default, and

Option 2 will supply participants with 50  $\mu\text{g}$  mini-tablets only upon request by investigator, if study treatment is to be taken with soft food or dispersed in apple/ orange juice.

The up-titration will be agreed upon during scheduled telephone calls or visits.

At Week 12 the iMTD for each participant will be determined. This dose should be kept unchanged until Week 16.

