## 7.2.5 Pharmacokinetic assessments

### 7.2.5.1 Pharmacokinetic assessments

PK blood sampling will be done:

- During the first week of study treatment (PK samples will be collected in the first 5 participants treated in Cohorts 1 to 3 at the following time points: pre-dose, 1, 2, 4, 6, 8, and 12 hours post-morning dose of selexipag (participants should have been on the same dose and mode of administration for at least 3 days in order to reach steady state).
- During the up-titration period,  $C_{\text{trough,ss}}$  PK samples will be collected in all participants prior to dose escalation at Day 15, and Weeks 4 and 6 (participants should have been on the same dose and mode of administration for at least 3 days in order to reach steady state).
- In each cohort, for participants who did not provide samples during the first week of study treatment, PK samples will be collected at Week 12 at steady state at the following time points: pre-dose, 1, 2, 4, 6, 8, and 12 hours post-morning dose of selexipag (participants should have been on the same dose and mode of administration for at least 3 days in order to reach steady state).

For the participant's convenience, an overnight stay at the site may be required before and/or after the PK profile sampling visit.

In total, 10 PK samples (1.2 mL blood/sample) will be collected per participant. The total amount of blood collected from each participant will be 12 mL. This is in accordance with general recommendations that the total blood volume collected within 24 hours for the purpose of a trial in children should not be more than 1%–5% of total body blood volume. Children are assumed to have 75–80 mL blood / kg body weight; i.e., a 9 kg infant is considered to have approximately 720 mL of total blood volume.

Blood sampling will take approximately 1 minute. [Table 4](#) displays the time points at which the PK samples will be taken.

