## **10 STATISTICAL METHODS**

All statistical analyses will be conducted by the Sponsor or by designated contract research organizations (CROs) supervised by the Sponsor.

A Statistical Analysis Plan (SAP) will provide full details of the analyses, data displays, and algorithms to be used for data derivations. All statistical analyses will be performed by age cohort and overall.

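### The dose-proportionality power model in Protocol 10.3.3 names no body-weight term, so the overall fit would give a slope below 1 even if PK were exactly proportional

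*Protocol*

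**What the plan says.** Protocol 10.3.3 states that proportionality of AUCtau,ss and Cmax,ss "of selexipag and ACT-333679 will be explored by the power model as described by" a cited report. It gives no covariate, stratum, interval level or acceptance criterion. The sentence just before it, on the non-compartmental parameters, says they "will be listed and summarized by dose and body weight cohort". Section 10 adds a general rule: "All statistical analyses will be performed by age cohort and overall".

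The analysis has a stated purpose. Section 3.2 says of the proportionality seen in adults: "It is assumed that the PK are also dose proportional in the pediatric population, and this will be further evaluated in the proposed study". The same section bases the ratio of paediatric to adult dose at every level, including the maximum, on proportionality.

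Three design features determine what the slope can show:

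- **Tiers (Sections 3.1 and 3.2).** Starting doses are 100, 150 and 200 µg for 9 to <25, 25 to <50 and ≥50 kg. The dose-weight relationship is "used to define body weight categories and starting dose for each body weight category such that on average the exposure" is comparable to that in a 70 kg adult.
- **Titration (Section 5.1.4).** "The maximum dose allowed to be administered will be 8-fold the corresponding starting dose".
- **Sampling (Section 7.2.5.1).** Each child gives one 12-hour profile. It is taken in Week 1 at the starting dose (the first 5 participants, read here as 5 per cohort) or at Week 12. For troughs, "PK samples will be collected in all participants prior to dose escalation at Day 15, and Weeks 4 and 6".

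SAP Section 1 leaves PK analyses to separate plans, which are not among the documents reviewed.

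**The concern.** With one AUC and one Cmax per child, the power-model slope rests entirely on differences between children. Part of the dose difference between children is a weight difference: from the lightest to the heaviest tier the dose doubles while exposure, by design, stays about level. A regression of log exposure on log dose without weight reads that level stretch as exposure failing to keep pace with dose, and the slope is pulled below 1.

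The stake is moderate. This is the named check of an assumption behind the increments and maximum dose in every tier. A slope near 0.85 whose interval excludes 1 could be reported as less-than-proportional PK in children when nothing of the kind is present.

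**Working it through.** The plan gives no figure for the power model, so there is none to reproduce.

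**Weight exponents.** Section 3.2 compares 51 kg and 96 kg adults with a 70 kg adult. With exposure proportional to weight^(−e):

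- ACT-333679: ln 1.2 / ln(70/51) = 0.58; ln 0.9 / ln(70/96) = 0.33.
- Selexipag: ln 1.3 / ln(70/51) = 0.83; ln 0.8 / ln(70/96) = 0.71.

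A log-log line through the tier doses at 17, 35 and 59 kg (the mid-weights in Appendix 7) has slope 0.56. At e = 0.576, exposure at those weights relative to 70 kg on 200 µg is 1.13, 1.12 and 1.10. The tiers do equalise exposure.

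**Analytic size.** Write dose = s × k, with s the tier starting dose and k the titration multiple. If clearance is proportional to s, k is independent of tier and PK is exactly proportional, the overall slope without weight is

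Var(ln k) / [Var(ln k) + Var(ln s)].

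For equal thirds at ratios 1 : 1.5 : 2, Var(ln s) = 0.0808. With one third of profiles at k = 1 and two thirds at k = m, Var(ln k) = (2/9)(ln m)²:

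- m = 8: 0.961 / (0.961 + 0.081) = 0.92
- m = 4: 0.427 / (0.427 + 0.081) = 0.84
- m = 2: 0.107 / (0.107 + 0.081) = 0.57

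With the two thirds spread evenly over 1 to 8 times, the slope is 0.89.

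**Simulation.** Inputs: 15 children per cohort; weights from a beta(2,2) distribution on the Appendix 7 ranges (10–24, 15–55, 28–90 kg); 5 profiles per cohort at the starting dose and 10 at the iMTD; AUC = dose × (weight/70)^(−e) × random effect; true slope exactly 1. The documents do not give the iMTD distribution; it is assumed uniform over 1 to 8 times. With log-scale SD 0.5 (an assumption; Appendix 7 gives 0.6 for adults):

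| e | Slope, no weight | 95% CI covers 1 | Slope with ln(weight) |
|---|---|---|---|
| 0.33 | 0.94 | 90% | 1.00 |
| 0.455 | 0.91 | 86% | 1.00 |
| 0.576 | 0.89 | 83% | 1.00 |
| 0.75 | 0.85 | 76% | 1.00 |
| 0.83 | 0.84 | 73% | 1.00 |

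With SD from 0.46 (an assumed lower value) to 0.60, the slope without weight is 0.84 to 0.94. A 90% interval covers 1 in about 58% to 85% of trials; with ln(weight) it covers in about 90%. Weight-category intercepts do as well. Changing the iMTD assumption at SD 0.5 widens the range: everyone at 8 times gives 0.88 to 0.95, and uniform over 2 to 6 times gives 0.79 to 0.92.

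**Within age cohort, no weight term.** Slopes are about 0.96 to 1.00, because Cohort 3 lies in a single tier and the others span fewer weights. The SD of the slope is about 0.15 to 0.2, or roughly ±0.3 to ±0.4 as a 95% interval.

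**If iMTD depends on exposure.** Suppose lower-exposure children titrate higher, at an assumed correlation of 0.7. The weight-adjusted slope is then about 0.76 to 0.82. Weight adjustment does not cure this second effect.

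**The case against.** The strongest reply is that the protocol never says the tiers are pooled or that weight is left out. The neighbouring summaries are by dose and body weight cohort, and a weight-adjusted or tier-stratified power model would satisfy the text. The PK plans not reviewed may already specify one. This stands: the finding is an omission in 10.3.3 and not a stated wrong choice. It does not dispose of the point, because the body-weight grouping belongs to the descriptive summaries, while Section 10 asks for an overall analysis. A literal reading gives the biased fit.

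Second, the age-cohort fits that Section 10 also requires are nearly free of the weight bias. That stands too, but 15 profiles each are too few for them to settle the question.

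Third, nothing is decided on this slope. No criterion is attached to it, and the dose-confirmation rules in Section 3.1 use the population PK model, which includes body weight and (Appendix 7) also uses the trough samples. This limits the consequence.

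A reader might infer that the study will report less-than-proportional PK, or that the slope will fall far below 0.8. The documents support neither. The first depends on how the fit is specified. The second needs either a link between iMTD and individual exposure, whose strength no document gives, or Week 12 doses clustered low.

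**Conclusion.** The concern holds as an under-specified analysis. An overall power model without body weight is biased below 1 under exact proportionality, to about 0.84 to 0.94, with 90% interval coverage of about 58% to 85%. These figures rest on the Section 3.2 adult exponents extended to children's weights, on the Appendix 7 weight ranges, on the SD range of 0.46 to 0.60, and on the assumed uniform iMTD. They were worked for AUC. The documents give no weight exponent for Cmax; the direction is the same if Cmax falls with weight.

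It would be wrong to infer that dose confirmation or the primary endpoint is compromised. The power model is a secondary, exploratory look, and the model-based exposure accounts for weight.

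**What to change.** In Protocol 10.3.3, or in the PK analysis plan with a cross-reference, specify for each analyte and for both AUCtau,ss and Cmax,ss:

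ln(parameter) = β0 + β1 ln(dose) + β2 ln(body weight) + error,

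or the same model with weight-category intercepts in place of β2. Report β1 with its confidence interval and state the level. Keep the age-cohort fits as descriptive.

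State one limitation: the slope compares different children, so if those with lower exposure titrate higher, β1 stays below 1 even after weight adjustment (about 0.76 to 0.82 at an assumed correlation of 0.7).

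As a supportive analysis only, fit a power model of ACT-333679 trough concentration on log dose with a random participant intercept, using the Day 15, Week 4 and Week 6 samples. This uses dose changes within a child. Its limits should be stated: the nominal doses at those visits are 2, 4 and 6 times the starting dose (Tables 1 to 3), at most a 3-fold range; dose rises with time; and trough is not AUC. It suits the metabolite (half-life 6.2–13.5 h) better than selexipag. With a half-life of 0.8–2.5 h, a 12-hour selexipag trough lies about 5 to 15 half-lives after the dose and may fall below the 0.01 ng/mL limit of quantification.

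The cost is analysis-plan wording. Weight, doses and samples are already collected. If the separate PK plan already includes weight, a cross-reference is enough.

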#### ~~10.3.4~~ Exploratory pharmacokinetic / pharmacodynamic analysis

The population PK/PD model will be built based on individual predictions of steady-state exposure for iMTD based on the final population PK models for both selexipag and ACT-333679. More details on PK and PD analyses will be in the modeling data analysis plan.

#### 10.3.5 Analysis of the safety variable(s)

All analyses of safety variables will be carried out descriptively using the Safety Analysis Set and will be performed as follows:

- In the overall population.
- By iMTD dose groups.
- By age cohort.

The iMTD is defined as the last dose received before the Week 12 visit (for participants who prematurely discontinued study drug) or the dose received on the day of the Week 12 visit (for participants who completed the 12-week up-titration period).

Safety data will also be explored by age cohort and by iMTD dose groups if a sufficient number of participants allows.

##### 10.3.5.1 Treatment-emergent adverse events

The number and percentage of participants with at least one TEAE / TESAE / AE leading to study treatment discontinuation will be described by system organ class (SOC) and

---

 The geometric mean of  $t_{max}$  and its 95% CI will not be calculated.

preferred term (PT) up to EOT + 3 days, and separately for the up-titration period (up to Week 12) and the maintenance phase (> Week 12 up to EOT + 3 days).

The same analysis will be performed according to the maximum intensity of reported AEs and according to the relationship to the study drug.

Listings will be provided for all reported AEs, including SAEs. In addition, separate listings will be provided for all AEs leading to premature discontinuation of study drug, and for all AEs leading to death.

